- Patients declining ICDs expressed concerns that the numbers didn't apply to them and/or the benefits were not enough: "It's like walking around with a motorcycle helmet on when you're driving your car." One patient addressed the trade-off between dying sooner from sudden death and living longer and dying of progressive heart failure: "Going into my decision is also the fact that I can't work because of my medical condition. I can't work at the hospital; I can't work at the church. My life is sitting here and watching TV... to take a defibrillator would just lengthen the process that I don't really want lengthened."
- Behavioral economics were applied via a framework analysis of two sets of interviews. We found evidence of cognitive bias in decision making, including patients attributing a halo effect to a clinician, who then presents a status quo bias to perform an ICD in the context of influential framing techniques. Taken together, the biases appeared to encourage ICD treatment.(under review)

Development of a measure of decision quality: Decision quality is an essential element of the Ottawa Decision Support Framework (Figure 2) defined as "the extent to which the implemented decision reflects the considered preferences of a well-informed patient."⁵⁵ Accordingly, a decision is "a quality decision" if the treatment chosen is concordant with a knowledgeable patient's values.^{55,56} Some have proposed that measures of decision quality be included in the pay for performance agenda⁵⁷ and the Affordable Care Act calls for "the development of quality measures that allow for the assessment of the experience, quality, and use of information provided to and used by patients..."³ We developed a measure of ICD decision quality using a robust process of patient and clinician assessment to determine the key knowledge items (content validity). We then tested this measure on a large population of patients and determined test-retest reliability ($r=0.56$, $p>.01$) and internally-reliable assessment of patient knowledge ($\alpha=.61$). We demonstrated discriminant known-groups validity of the knowledge measure by showing that clinicians scored better than patients with ICDs who scored better than patients without ICDs (98% vs. 60% vs. 40% mean scores, respectively).

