2. Non-English speaking (decision aids and study assessments are in English only currently)
3. Unable to consent
4. Currently has a left ventricular assist device (LVAD)
5. Prisoners

Given that the PtDAs and study assessments are in English, we must limit recruitment to English speaking patient participants. However, the paper tool will also be available in Spanish and we will measure whether this facilitated implementation among this group using aggregate measures. As we do not have the resources to enroll every patient at every site, we will enroll a subset of eligible patients. Specifically, we will ask each site to enroll the first ~6 patients each month, or until at least 6 patients are enrolled per month. While not completely random, there is also no systematic reason why demography would differ. This approach allows each site-PI to meet their aim of 50 enrolled patients per year without going over and maintaining awareness if they are under-target. A lesson learned from the DECIDE-LVAD trial is that without this constriction, over-enrollment is possible. If the site researcher is not able to enroll up to 6 patients in the first week of the month, then s/he may continue to approach patients until 6 have been enrolled that month.

Setting: We propose a 7-hospital trial (**Table 3**). Each site investigator is a practicing electrophysiologist within the setting. In addition to access to patients, each has research expertise in the area of ICDs in his/her own right. This proposal has already benefitted from strong engagement by all sites in crafting the PtDA and the proposal. A multi-site design affords many advantages:

- Aim 1: Conducting the trial at multiple sites avoids biases that could confuse the results. If conducted at a single center, it would be difficult to determine which changes in the decision process were due to the PtDAs versus those that were happening regardless (secular trends). Multiple sites allow for sequential transition of hospitals to the PtDAs (stepped-wedge design, see Table 4), thereby allowing for changes to the PtDA to be teased out from changes occurring in the background.
- Aim 2: Individual programs have diverse policies, providers, and institutional cultures that reflect the

Site	ICD Volume
University of Colorado Hospital	200
Denver Health Medical Center	70
The Denver VA Medical Center	100
Providence Health, Oregon	300
Baptist Health	87
Beth Israel	250
Mid America Heart Institute	350

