hospital and surrounding community. Testing the PtDAs in multiple programs across the U.S. can help determine how well the PtDA would disseminate to other hospitals.

C. Study Design and Research Methods

Overview: We propose a type II effectiveness implementation hybrid trial⁴¹ of our suite of ICD PtDAs. Our pragmatic design will allow us to simultaneously assess real-world effectiveness (Aim 1), and implementation (Aim 2).

Site	Baseline (1 year)	Intervention rollout sequentially across all sites (3 years)							Follow-up (1 year)
Random Site 1									
Random Site 2									
Random Site 3									
Random Site 4									
Random Site 5									
Random Site 6									

We will use a 6-site stepped-wedge design, with implementation guided by normalization process theory and evaluation guided by the RE-AIM framework (reach, effectiveness, adoption, implementation, and maintenance).⁸³⁻⁸⁵ For the purpose of this study, and as discussed with our grant proposal team, we will include 2 hospitals as one site during randomization in order to meet demographic requirements. As such, the University of Colorado Hospital and Denver Health Medical Center will be considered 1 site. We have 7 diverse sites (3 academic, 2 private, 1 county hospital, and 1 Veteran’s Affairs hospital) to allow us to explore broad contextual issues related to implementation variation. Sites all begin in the control phase, where usual care consists of the current education, decision making, and informed consent process. When sites reach their randomly assigned time to transition to the intervention, we will travel to the site to conduct the implementation. The pamphlet and video PtDAs will be formally integrated into the existing process. In both pre- and post-phases, we will enroll patients and survey them prior to their ICD decision and then again at 1 month and 6 months post-decision to determine the intervention’s effect on decision quality and a host of secondary outcomes. These patient-centered outcomes will be compared before and after implementation to determine intervention effectiveness. We will also survey clinicians and staff before, during, and after implementation of the intervention. In the broad view, this study will inform the science of decision support implementation for many interventional therapies in cardiovascular disease.

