Stepped-wedge multicenter trial (Table 3): We considered three potential designs for this trial. A classic patient-level randomization is not possible since programs (rather than patients) are effectively the primary targets of intervention implementation. The traditional cluster randomized trial would be disadvantaged by the small number of sites. Therefore, we propose a multicenter trial that is randomized at the clinic-level for a phased rollout of the shared decision support intervention.^{42,84} A variant of the cluster trial design, the stepped-wedge trial design is a one-way crossover cluster trial where all the groups will receive the intervention, but the time of intervention is randomly ordered. It is a compelling choice of design when 1) one of the goals is to study intervention implementation, 2) the intervention is thought to be efficacious, 3) all sites wish to receive the intervention and continue its implementation after the trial if it is effective, and 4) contamination/diffusion of the intervention effects to other subjects is likely. The stepped-wedge design is more efficient in terms of statistical power when compared to the classical cluster randomized design because the impact of the intervention is estimated using both within and between cluster differences.

Table 5: Measures	Baseline Pre Decision	1 Month Post Decision	6 Months Post Decision
-------------------	-----------------------	-----------------------	------------------------

COVARIATES			
- Demographics (combined survey and short chart review)	X		
- Medications, Comorbidities, Heart Failure Type/Severity	X		X
- Literacy (REALM-R 7 item) ⁸⁵ and Subjective Numeracy ⁸⁴	X		
EFFECTIVENESS OUTCOMES (see descriptions below)			
- Decision Quality – Knowledge	X	X	X
- Decision Quality – Value-concordance	X	X	X
- Decision Process		X	X
- Decision choice		X	X
- Self-Efficacy Scale	X	X	X
- Control Preferences	X	X	X
- Decision conflict	X	X	X
- Decision regret		X	X
- PHQ-2	X		X
- GAD-2	X		X
- ICD Experiences (+/- shock; +/- complications etc.)		X	X

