Stepped-Wedge Trials are difficult logistically: For all of their associated advantages, stepped-wedge designs are not without challenges including logistical management of multiple sites in varying stages of implementation over time, the possibility of treatment diffusion (to patients initially seen during the control period but receiving follow-up care during the intervention), and the requirement that all sites begin and end evaluation at the same times. Fortunately, Drs. [name] & [name] both have experience with this design in a recent trial assessing implementation and effectiveness of PtDAs for ventricular assistance device therapy.⁴² Also, the baseline survey combined with the importance of getting all sites to start at the same time is why we've included a year of start-up time.

Enrolling 900 patients is overly optimistic: Each site will be expected to enroll 50 patients per year. Because we are implementing a suite of PtDAs, we expect no trouble enrolling the appropriate amount. In our pilot trial at the site with the lowest volume (the Denver VA) we enrolled 9 patients in 6 months for only the initial implant decision aid. We learned that there were many patients getting reimplantation and CRT devices whom were missing. With the suite of PtDAs available in this trial, we think we'll have no trouble enrolling the eligible amount of patients. Also, with our experience with the DECIDE-LVAD trial, we are having more trouble with over-enrollment which is only a problem in rebudgeting to reimburse sites per patient.

What if the study is not successful? If the study does not meet its primary endpoint, our formative evaluation will provide information about potential reasons that it was not successful and lead to better studies of alternative dissemination and implementation strategies for advanced progressive illness. In a pragmatic design such as this, most of the threats (e.g. low reach, low implementation) bias to the null. Indeed, this is precisely why this is a more interesting study than doing a research staff controlled efficacy trial.

How will the PtDAs stay Up-To-Date and Responsive to Perceived Needs? Given the rapid changes in ICD technology, the PtDAs must be kept current to maintain relevance. This will be accomplished via:

- Annual reviews of literature: With incorporation of important changes into the PtDAs.

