- Modular design: The sectional build of the PtDAs—clearly defined pages for the pamphlet and segmented video—allows for simple revision as problems are identified or information changes over time.

F. Data Analysis Plan:

Quantitative analysis (Hypotheses 1a, 1b, 1c): The analyses of the effectiveness will use a repeated measures mixed model. This strategy allows for partially incomplete data (e.g. missing follow-up or one of the collection periods) and relaxes the missing data assumptions to missing at

random conditional on observed data. Prior to these analyses, we will contrast the participants in the 2 phases of the study, identifying any patient/site characteristics that are unbalanced. If more than 3-5 variables are identified, we will develop a propensity score for the likelihood of being in the intervention phase. Each analysis model will include an indicator variable for the intervention phase, indicators for each of the sites and the variables identified above.

Sample Size and Power Calculation: This trial was designed to have diversity in implementation settings. As such, to effectively be powered to explore implementation across diverse settings, we are overpowered to test our primary quantitative outcomes (the knowledge domain of decision quality). With a sample size of 900 patients and a standard deviation of 18%, achieved power would approach 1.00 to detect a 10% improvement in knowledge (in the 2011 Cochrane Review, knowledge improved an average of 13.8%, in our pilot trial, knowledge improved 12%).⁶ Even with variance inflation for correlation within sites (assuming intraclass correlation 0.01), the power remains good at 0.98. This level of power will afford the ability to assess some heterogeneity of effect across sites and vulnerable patient groups, as well as adequate assessment of secondary effectiveness measures and implementation evaluation. To test the hypothesis that better informed patients will have less anxiety (hypothesis 1c), we will correlate the knowledge score with the HADS- A. Using a Pearson's correlation coefficient, for a sample size of 300 (based on 1/3 illustrating significant anxiety) then the person's correlation is 0.18 for a power of 90% and an alpha of 0.05.

G. Summarize Knowledge to be Gained:

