We have designed the implementation to use and leverage existing resources to implement the intervention. Further, we have designed the study as an effectiveness/implementation study with emphasis on formative evaluation. Together, it is our hope that if the intervention is successful, we will develop an implementation guide and online distribution of materials for other ICD programs and other practitioners interested in testing and disseminating effective therapies.

The lessons learned herein will apply broadly. As discussed in the Significance section, policies are changing. Patients are increasingly demanding involvement and seeking additional sources of information. The PtDA development group in Colorado has been contracted by the American College of Cardiology to develop a PtDA for patients with severe aortic stenosis considering surgical versus transcatheter repair. The American College of Cardiology has also inquired with Colorado about developing a tool for the recently approved left atrial appendage occlusion device. Science on real-world effectiveness and implementation is essential in informing the field of PtDA delivery for high risk medical conditions.

H. Bibliography & References Cited:

1. Alston, C. Shared decision-making strategies for best care: Patient decision aids: The Institute of Medicine; 2014.
2. The Institute of Medicine. Crossing the Quality Chasm: A New Health System for the 21st Century. Washington D.C.: National Academy Press; 2001.
3. The Patient Protection and Affordable Care Act. 2010.
4. Patient Preference Information. The Food and Drug Administration, 2015. (Accessed 05/24/2016, at <http://www.fda.gov/downloads/MedicalDevices/DeviceRegulationandGuidance/GuidanceDocuments/UCM446680.pdf>.)
5. Decision Memo for Screening for Lung Cancer with Low Dose Computed Tomography (LDCT) Centers for Medicare and Medicaid Services; 2015.

6. Proposed Decision Memo for Percutaneous Left Atrial Appendage (LAA) Closure Therapy. Centers for Medicare and Medicaid Services; 2015.
7. Tuckett D. et al. Meeting Between Experts: An Approach to Sharing Ideas in Medical Consultations. London: Tavistock Publications; 1985.
8. Rosenbaum L. The Paternalism Preference--Choosing Unshared Decision Making. *N Engl J Med* 2015;373:589-92.

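### The effectiveness models state no calendar-period term, so as written they cannot separate the decision aids from secular trend

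*Combined protocol and SAP*

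**What the plan says.** Section IV.F plans a repeated measures mixed model and then states its terms: "Each analysis model will include an indicator variable for the intervention phase, indicators for each of the sites and the variables identified above". The preceding sentences define those variables as patient or site characteristics that differ between the two phases, to be replaced by a propensity score if there are many. No term for calendar period, step or enrolment date appears there or elsewhere in the protocol text supplied.

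The design sections promise more. Under Setting in section IV.B, the case for several sites crossing over in sequence is that this separates the intervention from secular trends, "thereby allowing for changes to the PtDA to be teased out from changes occurring in the background". Section IV.C (Stepped-wedge multicenter trial) says the design is efficient "because the impact of the intervention is estimated using both within and between cluster differences". The Overview in the same section, however, describes a simpler comparison: "These patient-centered outcomes will be compared before and after implementation to determine intervention effectiveness".

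**The concern.** In a stepped wedge, phase and calendar time are confounded within every site: control patients come first and intervention patients later. With only phase and site indicators, the phase coefficient pools the within-site changes, and any background change in knowledge, education or usual care goes into it. Upward drift would be reported as a decision-aid effect, and downward drift would mask a real one. The contrast between sites in different phases at the same calendar time, which the staggered rollout exists to provide, is not used.

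The protocol gives reason to expect change. Section IV.G says policies are changing, and adds: "Patients are increasingly demanding involvement and seeking additional sources of information". The problem affects every phase comparison, including the primary outcome. It is sharpest for outcomes with no baseline measurement in Table 5: decision process, decision choice, decision regret and ICD experiences.

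**Working it through.** **Inputs from the protocol.** N = 900, SD 18 points, target difference 10 points and ICC 0.01 (IV.F); six randomised units (IV.C); "Each site will be expected to enroll 50 patients per year" and "the requirement that all sites begin and end evaluation at the same times" (IV.E). Then 6 × 50 × 3 years = 900.

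**Assumptions.** Even enrolment; seven equal periods with one site crossing after each of the first six; 150 patients per site and 900/42 = 21.43 per site-period cell; two-sided 5% tests (IV.F states alpha only for hypothesis 1c); linear drift of 0.5, 1 or 2 points per year. The documents give no drift rate.

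**The plan's own power figure.** Unclustered, SE = 18 × √(2/450) = 1.20, and power for 10 points exceeds 0.9999. With design effect 1 + 149 × 0.01 = 2.49, SE = 1.20 × √2.49 = 1.89, and power is 0.9996 (normal), 0.985 (t, 5 df) or 0.970 (t, 4 df). This agrees with the stated values near 1.00 and of 0.98. The calculation contains no period adjustment.

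**Bias, one score per patient.** If a site enrols evenly from 0 to 3 years and crosses at c, mean enrolment time is c/2 in control and (c + 3)/2 in intervention. The gap is 1.5 years whatever c is, so drift of d per year adds 1.5d to the phase coefficient.

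**Standard errors.** Residual variance is 0.99 × 18² = 320.76. The sum of squares of the phase indicator over the 42 cells is 8 after removing site means, and 3.333 after removing site and period means.

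- Without period: √(320.76/(21.43 × 8)) = 1.368
- With period: √(320.76/(21.43 × 3.333)) = 2.119

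**False-positive rate without period**, Φ(b/1.368 − 1.96) + Φ(−b/1.368 − 1.96):

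| Drift per year | Bias b | Rate |
|---|---|---|
| 0 | 0 | 5% |
| 0.5 | 0.75 | 8.5% |
| 1 | 1.5 | 19.5% |
| 2 | 3.0 | 59% |

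If all seven hospitals enrol 50 a year, enrolment takes 900/350 = 2.57 years, the gap is 1.29 years and the rates are about 7.5%, 15–16% and 45–48%. If enrolment ran for all five years of the design table, the gap would be 2.5 years.

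**Using the repeated scores.** IV.F does not say which visit contrast is the effect. Section III reports on the knowledge instrument, "We then tested this measure on a large population of patients and determined test-retest reliability", with r = 0.56. I borrow that as the correlation between visits, which is an assumption. At 1 point per year:

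- *One phase coefficient over all three scores.* SE = √(320.76 × (1 + 2 × 0.56)/3 / 171.43) = 1.150, where 171.43 = 21.43 × 8. If drift is common to all visits, bias is 1.5 and the rate 26%. If it arises only after baseline, bias is 2/3 × 1.5 = 1.0 and the rate 14%.
- *Phase-by-visit contrast, site main effects.* The variance of a follow-up minus baseline difference is 2 × 0.44 × 320.76 = 282.27, so SE = √(282.27/225) = 1.120, where 225 = 900 × 0.25. Drift shared by baseline and follow-up cancels. Drift arising after baseline enters with weight 12/10.5 = 1.143 years, the pooled gap in enrolment time (1.5 years with site-by-visit terms). With none, half or all of the drift after baseline, bias is 0, 0.57 or 1.14 points and the rate 5%, 8.0% or 17.5%.

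**Does a period term remove it?** In the one-score model, period indicators take the linear-drift bias to zero. In the phase-by-visit model, period main effects leave the 1.143 unchanged; period-by-visit terms take it to zero.

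**Simulation.** Patient-level simulation with random enrolment dates, 2,000 runs per scenario, gave 8.8%, 19.1% and 56.7% for the one-score model without period at 0.5, 1 and 2 points per year. With the appropriate period terms the rate was 3.7–6.0% in every scenario and mean bias was under 0.1 points.

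**The case against.** The best reply is that the list of terms is incomplete, not wrong. A repeated measures model needs visit terms and a within-patient covariance, and the sentence names neither, so a period term may simply have been left out. That is possible. But visit time counts from enrolment, not by calendar. An enrolment date is not naturally a patient or site characteristic, and covariate balance does not remove a trend in usual care. The omitted term is the one on which the stated reason for the design depends. An analyst who followed the text would get a biased estimate under drift.

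A second reply is that baseline knowledge is measured, so a phase-by-visit contrast would cancel shared drift. That stands in part: the bias is then zero for shared drift and at most 1.14 points at 1 point per year in the site-main-effects version. But the plan specifies no such contrast, and the outcomes without a baseline cannot use one.

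Third, the figures are conditional. The drift rates are assumed, and section IV.G is arguing for wide applicability, not forecasting knowledge scores. The value r = 0.56 is a test-retest reliability; moving r from 0.3 to 0.8 takes the 17.5% rate from about 13% to 33%. On 4 df the one-score rates would be 7%, 14% and 39%. The normal figures are kept because a patient-level model with fixed site indicators has hundreds of residual degrees of freedom. None of this changes the direction of the problem.

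**Conclusion.** The concern holds and must be fixed. As written, the models give a within-site before/after estimate that cannot deliver the separation from background change claimed in section IV.B, and they do not use the between-site information claimed in section IV.C. The fault lies in the written analysis, not in the design: staggered crossover makes period effects estimable.

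The size depends on a drift rate the documents do not give and on a visit contrast they do not fix. At 1 point per year the bias ranges from 0 to 1.5 points across the models above under the 3-year layout, with false-positive rates from 5% to 26%. Modest drift would not explain a full 10-point effect. It would still bias the estimate, and section IV.F also relies on the surplus power for secondary outcomes and heterogeneity, where effects may be smaller. With zero drift and no site-by-period variation the rate is the nominal 5%.

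**What to change.** In section IV.F, pre-specify fixed effects for calendar period, defined by enrolment date, in every model that compares phases. State the visit contrast that defines the effect. If it is phase-by-visit, add period-by-visit terms as well, because period main effects alone leave that contrast unchanged. In section IV.C, describe the effect as adjusted for secular trend instead of as a before/after comparison. Restate power for the adjusted model.

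No new data are needed: the 1- and 6-month questionnaires are already timed from enrolment. The cost is precision (3-year layout; r = 0.56 for the contrasts; 5-point power on the normal distribution):

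| Model | SE without → with period terms | Power for 5 points |
|---|---|---|
| One score | 1.37 → 2.12 | 0.955 → 0.655 |
| Phase-by-visit, site main effects | 1.12 → 1.50 | 0.99 → 0.91 |
| Phase-by-visit, site-by-visit effects | 1.28 → 1.99 | 0.97 → 0.71 |

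Power for 10 points remains 0.997 (normal) or 0.93 (4 df) with one score, and at least 0.957 on 4 df for the contrasts. The primary target is affordable; the claim of ample power for smaller effects needs revising.

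### With six randomised units, no listed model term carries site variation in the effect, or over time, into the standard error, so intervals can be too narrow

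*Combined protocol and SAP*

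**What the plan says.** Section IV.C states "We will use a 6-site stepped-wedge design". There are seven hospitals but six randomised units, because "the University of Colorado Hospital and Denver Health Medical Center will be considered 1 site".

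Section IV.F says "The analyses of the effectiveness will use a repeated measures mixed model" and gives tolerance of incomplete data as the reason. On content it says: "Each analysis model will include an indicator variable for the intervention phase, indicators for each of the sites and the variables identified above". The variables referred to are those found unbalanced between phases, or a propensity score in their place. The section does not give the random effects, the covariance structure, the degrees of freedom or a variance estimator.

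The power paragraph of Section IV.F starts "With a sample size of 900 patients and a standard deviation of 18"% and aims "to detect a 10% improvement in knowledge". It allows for an intraclass correlation of 0.01, reports power of 0.98, and says this leaves room to "assess some heterogeneity of effect across sites and vulnerable patient groups". No variance for that heterogeneity is given. The Aim 2 bullet under Setting (Section IV.B) hopes to learn "how well the PtDA would disseminate to other hospitals".

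**The concern.** Site indicators remove constant differences in level between sites. They do not allow for two other sources of variation: the intervention may work better at some sites than others, and a site's mean may drift from period to period for local reasons. Patients in the same site and phase share both, so neither averages out as more patients are enrolled. With six units, the information about them is worth only about 4–5 degrees of freedom.

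If the phase coefficient is tested against patient-level error, the reported standard error stays the same however large this variation is. A chance pattern in one or two sites could then look like an effect of the decision aid, and the interval would claim more precision than six sites can give. Period terms are needed for secular trend, but they do not cure this.

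**Working it through.** **Inputs.** From Section IV.F: 900 patients, SD 18 points, effect 10 points, ICC 0.01, power 0.98. From Section IV.C: six units. Assumed: 900/6 = 150 patients per unit, seven equal periods with one unit crossing at each step (the cells of the schedule table could not be read), one outcome per patient, no secular trend, and two-sided alpha 0.05 (the plan states 0.05 only for the hypothesis 1c correlation).

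**1. The plan's power.** Design effect = 1 + (150 − 1) × 0.01 = 2.49. Effective N = 900/2.49 = 361. SE = 18 × √(4/361) = 1.89, and 10/1.89 = 5.28. A normal calculation gives power 0.9996. Noncentral t gives 0.970 on 4 df and 0.985 on 5 df. The stated 0.98 is reproduced within 2 percentage points, and the t versions bracket it.

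**2. SE that the listed model reports.** Patients per site-period = 150/7 = 21.43. After site means are removed, a unit with *a* of its 7 periods in intervention contributes a(7 − a)/7 to the sum of squares of the phase indicator. For a = 1 to 6 the total is 56/7 = 8. Variance = 18²/(21.43 × 8) = 1.89, so SE = 1.375.

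**3. Effect varying between sites with SD τ (assumed).** Each unit's weight is a(7 − a)/56, and the squared weights sum to 560/3136 = 0.1786. True variance = 1.89 + 0.1786τ². With period terms the sum of squares falls to 10/3 and the weights do not change, so true variance = 4.536 + 0.1786τ², while the model reports √4.536 = 2.130. Type I error = 2[1 − Φ(1.96 × reported SE/true SE)].

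| τ (points) | True SE, as listed | Type I error | True SE, with period terms | Type I error |
|---|---|---|---|---|
| 0 | 1.375 | 5.0% | 2.130 | 5.0% |
| 1 | 1.438 | 6.1% | 2.171 | 5.5% |
| 1.8 | 1.571 | 8.6% | 2.262 | 6.5% |
| 3 | 1.870 | 15.0% | 2.479 | 9.2% |

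Simulation of the listed model (8,000 trials per setting) agrees: analytic and simulated values together span 6.1–6.3%, 8.2–8.6% and 15.0% at τ = 1, 1.8 and 3. With period terms the simulated values were 5.5%, 6.4% and 8.6%. A separate simulation gave 9.7% at τ = 3.

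**4. No effect at any site, but site means vary by period (ICC ρ, assumed).** True variance = 324(1 − ρ)/(21.43 × 8) + 324ρ/8.

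- ρ = 0.0025: 1.885 + 0.101 = 1.987, SE 1.409, error 5.6%.
- ρ = 0.005: 1.881 + 0.203 = 2.083, SE 1.443, error 6.2% (simulated up to 6.6%).
- ρ = 0.01: 1.871 + 0.405 = 2.276, SE 1.509, error 7.4% (simulated 7.9%).

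**5. Coverage when the aid works.** In simulation with a true mean effect of 10 points (6,000 trials), the nominal 95% interval missed the average effect 5.0%, 9% and 15% of the time at τ = 0, 1.8 and 3. With period terms it missed 7% and 10% of the time at τ = 1.8 and 3.

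**6. Power with this variation allowed for.** With period terms, a site intercept (ICC 0.01) and a random intervention effect, the SE is 2.023 at τ = 1.8 and 2.268 at τ = 3. The ratios are 10/2.023 = 4.94 and 10/2.268 = 4.41. Noncentral t on 4–5 df gives power 0.95–0.97 and 0.90–0.94. Site-by-period variance is not included and would lower these.

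**7. Candidate methods.** A t-test on six within-site differences (5 df) held 4.7–5.6% in data without a secular trend. A leave-one-site-out jackknife t (5 df) held 3–5%. The permutation test held about 5% under the strict null, but rejected about 7–11% at τ = 3–4. The Kenward-Roger and Satterthwaite versions were not simulated.

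**The case against.** A reader might infer that the planned test simply has a type I error above 5%. The documents do not support that. Site indicators absorb constant site differences, so with an ICC of 0.01 and no other site variation the error is 5.0%. If the aid works at no site, there is no effect heterogeneity to inflate anything. The 15% figure concerns a different null, in which the aid raises knowledge at some sites and lowers it at others with an average of zero. This limits the claim and is accepted.

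Patient-level error is also an inference. Section IV.F leaves the random part open, and a power of 0.98 fits a calculation on 4–5 df. That stands too, but the analysis text names no such degrees of freedom, and the terms it does list would not supply them.

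The choice of target matters. The wish to generalise to other hospitals sits under Aim 2, and Section IV.F says heterogeneity can be assessed, not that it is expected. For inference to these six sites alone, effect heterogeneity does not invalidate fixed-effect errors. Site-by-period variation still does.

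Nor does the point extend to every secondary outcome: no outcome-specific variances are given, and the hypothesis 1c anxiety test is a correlation, not a phase contrast. Finally, an effect of the planned size would still be declared: 10/1.87 is about 5.3 at τ = 3, against a 5-df critical value of 2.57.

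**Conclusion.** The point holds as a conditional one. For six randomised units, no listed term or correction brings site variation in the effect, or in site means over time, into the standard error. Run as listed, the model reports an SE near 1.38 points when the true value could be 1.57 or 1.87 (τ = 1.8 or 3).

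The resulting error ranges from the nominal 5%, through about 6–8% under the strict null, to about 15% for a zero average effect at τ = 3 (9–10% with period terms). Every figure above 5% rests on an assumed variance and on the assumed equal-sized, one-site-per-step layout. An unconditional statement that the error exceeds 5% would go beyond the documents. The issue bears on the honesty of the intervals and on modest effects, more than on detecting a 10-point gain. It is a worthwhile, low-cost improvement.

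**What to change.** Amend Section IV.F for the phase contrasts as follows.

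1. Add period terms, and random site-by-period and site-by-phase terms, with Kenward-Roger or Satterthwaite degrees of freedom for the phase effect and its interval. State the full random and covariance structure, including repeated measures within patient.
2. Name a fallback in case six sites cannot support the variance components: a site-level t analysis on about 4–5 df. It should keep the period adjustment, for example a leave-one-site-out jackknife, because simple before-after differences do not handle secular trend.
3. Report, as support, a permutation test over the crossover orders actually possible under the schedule. It is exact only for no effect at any site, so it does not replace the small-df analysis.
4. State whether inference is to these six sites or to sites in general.
5. Restate the 0.98 power under this analysis: about 0.95–0.97 at an effect SD of 1.8 points and 0.90–0.94 at 3 points, with period terms and 4–5 df.

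This needs SAP wording and some analysis time, and no new data. The price is wider intervals and somewhat lower stated power, which a trial that describes itself as overpowered on knowledge can afford. The jackknife fallback is conservative: its simulated power for 10 points was 0.76–0.93, depending on heterogeneity.
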